5.5 Physical Examination

Physical examination will be performed at Visit 1 and 4. The following body systems will be examined: Gastrointestinal; Reproductive/Breast; Cardiovascular; Endocrine; General Appearance; Head, Eyes, Ears, Nose, Throat; Musculoskeletal; Neurologic; Peripheral Vascular; Psychiatric; Genitourinary/Renal; Respiratory; Dermatologic. Each system will be classified as Normal, Abnormal Not Clinically Significant (NCS) or Abnormal Clinically Significant (CS).

Number and percentage of subjects with each assessment result will be tabulated by body system, visit and treatment group, as well as both treatment group combined.

All results will be listed.

5.6 C-SSRS

Columba Suicide Severity Rating Scale (“Since Last Visit” version) will be administered at each scheduled visit.

Suicidal ideation will be defined as “yes” answer to any one of the five suicidal ideation questions (Question 1-5) on the C-SSRS.

Suicidal behavior will be defined as “yes” answer to any one of the 5 suicidal behavior questions (Actual attempt, Interrupted attempt, Preparatory Acts or Behavior, Suicidal behavior, Completed suicide) on the C-SSRS.

Number and percentage of subjects with any suicidal ideation and/or any suicidal behavior will be presented by visit and treatment group, as well as for both treatment groups combined.

Time from baseline to the first appearance of suicidal ideation or suicidal behavior will be summarized descriptively for those subjects who develop suicidal ideation or suicidal behavior during the study (i.e. do not have suicidal ideation or suicidal behavior at baseline, but report it during the study).

All results will be listed.

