17. APPENDICES

APPENDIX A. RECOMMENDATIONS FOR IPX203 DOSING

Subjects will be initially started on the final IPX203 dosing regimen that was determined during the IPX203 dose conversion period of Study IPX203-B16-02. Investigators are permitted to adjust the dosing regimen of IPX203 during this study to achieve the optimal balance of efficacy and safety and any dosing changes will be recorded at the study visit.

1. It is recommended that the subject takes IPX203 doses approximately every 8 hours apart (for example, a subject may take IPX203 at 6 AM, 2 PM, and 10 PM) with the exception that subjects who converted from a total daily dose of less than 125-500 mg IR CD-LD may take IPX203 every 12 hours. Some subjects may benefit from a shorter or longer dosing interval. The dosing interval may vary but should not be more frequent than every 6 hours.
2. The Investigator (or his/her staff) is advised to be in telephone contact with the subject, especially during the initial weeks of this study, to assess the need for dosage adjustment with the goal of minimizing “Off” time without causing troublesome dyskinesia or other dopaminergic side effects. Calls to the subject can be reduced when the subject reaches an acceptable stable dosing regimen.
3. If dose adjustment is necessary, consider the following options recognizing that the number of capsules at each dose may be varied to achieve an optimal response.
 - a. If turning “On” is slow following the first morning dose, consider taking the morning IPX203 dose in the fasted state and/or increasing the dose by one capsule (35-140 mg IPX203 CD-LD).
 - b. If turning “On” is slow later in the day or to reduce “end-of-dose” “Off” time, consider increasing the dose by one capsule (35-140 mg IPX203 CD-LD) before reducing the dosing interval.
 - c. In case of troublesome dyskinesias, consider reducing the dose by one capsule (35-140 mg IPX203 CD-LD) prior to increasing the dosing interval.
4. Initially, all subjects will be dispensed 2 capsule dosage strengths, one of which will be the 35-140 mg IPX203 CD-LD capsules. Following dose regimen stabilization, up to 2 capsule dosage strengths may be dispensed from those available (35-140 mg, 52.5-210 mg, 70-280 mg, and 87.5-350 mg IPX203 CD-LD)

**APPENDIX B. COLUMBIA-SUICIDE SEVERITY RATING SCALE
(C-SSRS)**

COLUMBIA-SUICIDE SEVERITY RATING SCALE (C-SSRS)

Since Last Visit

Version 1/14/09

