Has subject engaged in Non-Suicidal Self-Injurious Behavior? Interrupted Attempt: When the person is interrupted (by an outside circumstance) from starting the potentially self-injurious act (if not for that, actual attempt would have occurred). Overdose: Person has pills in hand but is stopped from ingesting. Once they ingest any pills, this becomes an attempt rather than an interrupted attempt. Shooting: Person has gun pointed toward self, gun is taken away by someone else, or is somehow prevented from pulling trigger. Once they pull the trigger, even if the gun fails to fire, it is an attempt. Jumping: Person is poised to jump, is grabbed and taken down from ledge. Hanging: Person has noose around neck but has not yet started to hang - is stopped from doing so. Has there been a time when you started to do something to end your life but someone or something stopped you before you actually did anything? If yes, describe:		
		Yes  No 
Aborted Attempt: When person begins to take steps toward making a suicide attempt, but stops themselves before they actually have engaged in any self-destructive behavior. Examples are similar to interrupted attempts, except that the individual stops him/herself, instead of being stopped by something else. Has there been a time when you started to do something to try to end your life but you stopped yourself before you actually did anything? If yes, describe:		
		Yes  No 
Preparatory Acts or Behavior: Acts or preparation towards imminently making a suicide attempt. This can include anything beyond a verbalization or thought, such as assembling a specific method (e.g., buying pills, purchasing a gun) or preparing for one's death by suicide (e.g., giving things away, writing a suicide note). Have you taken any steps towards making a suicide attempt or preparing to kill yourself (such as collecting pills, getting a gun, giving valuables away or writing a suicide note)? If yes, describe:		
		Yes  No 
Suicidal Behavior: Suicidal behavior was present during the assessment period?		
		Yes  No 
Answer for Actual Attempts Only		

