2 GENERAL CONSIDERATIONS FOR DATA ANALYSIS

The database will be locked and final analysis of the data will be performed after all subjects have completed the study, outstanding data queries have been resolved or adjudicated as unresolvable, and the data have been cleaned and finalized. The statistical analyses will be performed by Quartesian LLC, with approval of the Sponsor, using SAS Version 9.4 (or higher).

All tables, figures and listings will be produced in landscape format.

Subjects will be assigned to treatment group defined by the treatment the subject received in the double-blind phase of the previous study IPX203-B16-02 (IPX203 or IR CD-LD).

In general, all data will be listed by subject and visit/time point where appropriate. The summary tables will be stratified by, or have columns corresponding to, treatment groups. Total group will also be presented.

The total number of subjects in the treatment group (N) under the stated population will be displayed in the header of summary tables.

Data will be summarized using descriptive statistics for continuous variables. Unless otherwise specified, descriptive statistics will include number of subjects, mean, standard deviation, minimum, median and maximum. Number of subjects with missing values will also be displayed, but only if non-zero. The minimum and maximum statistics will be presented to the same number of decimal places as the original data. The mean and median will be presented to one more decimal place than the original data. The standard deviation will be presented to two more decimal places than the original data.

In summary tables of categorical variables, counts and percentages will be displayed. The count [n] indicates the actual number of subjects in a particular category, which should always be less than or equal to the total number of subjects

in the respective study group with known (non-missing) category [M]. Percentage will be obtained by: % = n/M*100. Unless otherwise specified, all percentages will be expressed to one decimal place.

In by-visit summaries, only data collected on scheduled visits/timepoints will be summarized. Data from unscheduled assessments will be included in listings and may be used in determination of baseline if applicable.

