2.3 Visit Windows

Generally data will be analyzed by nominal visit when the data was collected. However, if a subject does not have a particular data point for a certain scheduled visit, but instead has it for an

unscheduled visit that occurred within +/-14 days window of the planned date of the scheduled visit, then the data from the unscheduled visit will be used in place of the missing scheduled visit. This will apply to both the clinical utility and safety data.

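### SAP 5.6 gives suicidality percentages only by visit, with no any-time post-baseline percentage from all C-SSRS forms, so a positive unscheduled form can be left out

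*SAP*

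**What the plan says.** SAP 5.6 states that the C-SSRS "will be administered at each scheduled visit". The version used is "Since Last Visit" (Protocol Appendix B; SAP 5.6). The planned percentage table reads: "Number and percentage of subjects with any suicidal ideation and/or any suicidal behavior will be presented by visit and treatment group", with both groups also combined.

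The general rule in SAP 2 is "In by-visit summaries, only data collected on scheduled visits/timepoints will be summarized". It continues: "Data from unscheduled assessments will be included in listings and may be used in determination of baseline if applicable". SAP 2.3 makes one exception, for safety data as well: "if a subject does not have a particular data point for a certain scheduled visit" but has an unscheduled one within 14 days either side of the planned date, "then the data from the unscheduled visit will be used in place of the missing scheduled visit".

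SAP 5.6 has a second summary, the time from baseline to first suicidal ideation or behavior, among subjects negative at baseline who report it during the study. All C-SSRS results are also listed.

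SAP 5.6 counts completed suicide among the behavior items. The form reproduced in Protocol Appendix B has an overall item, "Suicidal behavior was present during the assessment period", and a lethality code for death under actual attempts, but no completed-suicide item.

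**The concern.** For a laboratory value or a blood pressure, the scheduled-visits rule costs one extra reading. A since-last-visit form is different, because each form covers only the interval back to the last contact. If an unscheduled form is given and the site treats it as the last visit, the next scheduled form can truthfully be negative. The unscheduled form may then be the only C-SSRS record of the event, and the percentage table does not use it.

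A second gap needs no unscheduled form. A reader of a long-term safety study wants the percentage of subjects with ideation or behavior at any time on open-label IPX203. The SAP plans no such figure, although the C-SSRS is a stated safety parameter (Protocol 12.1) and SAP 5.3 plans an any-time post-baseline count for orthostatic hypotension.

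**Working it through.** There is no planned figure to reproduce: the documents give no expected suicidality rate. The check traces each kind of record through SAP 2, 2.3, 2.4, 5.1 and 5.6.

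| Record | By-visit C-SSRS percentage | Other planned outputs |
|---|---|---|
| Positive scheduled or early-termination form | Included (SAP 2.4 gives early termination a Visit 4/ET row) | Listing; time-to-first if negative at baseline |
| Positive unscheduled form, scheduled form present | Not included | Listing; by its wording, eligible for time-to-first if negative at baseline |
| Positive unscheduled form, scheduled form missing, within 14 days | Included by SAP 2.3 substitution | Listing; time-to-first as above |
| Positive unscheduled form, scheduled form missing, outside 14 days | Not included | Listing; time-to-first as above |
| Non-fatal event between visits, no unscheduled form | Within the recall of the next scheduled form, so included if reported there | Listing; time-to-first as above |
| Suicide with onset no later than 1 day after last dose | Only if a form recording it is completed | Serious TEAE and TEAE leading to death (SAP 5.1) |
| Suicide with onset more than 1 day and up to 30 days after last dose | Only if a form recording it is completed | Reportable SAE (Protocol 12.3.2), outside the TEAE counts (SAP 5.1) |

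**Can the any-time count be rebuilt from the planned tables?** Let n2, n3 and n4 be the positive counts in the Visit 2, Visit 3 and Visit 4/ET rows. One subject may be positive in several rows, so the number A positive in at least one row is known only within limits:

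max(n2, n3, n4) ≤ A ≤ n2 + n3 + n4.

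Let U be the subjects positive only on unscheduled forms that enter no row. The any-time count is then A + U, and no table shows U.

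**Does the time-to-first summary supply it?** Under SAP 2 its descriptive statistics include a number of subjects, T. If it uses all forms, then A + U = T + B, where B is the number positive at baseline and again afterwards. B is not planned as an output. The SAP does not say whether unscheduled forms feed T, and it specifies no percentage for it.

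**Size.** With the approximately 300 subjects of SAP 1.3 as denominator, the any-time percentage rises by 100 × U / 300. One subject is 100 / 300 = 0.33 percentage points; U = 0 gives no difference. The documents give no value for U, and 300 is an enrolment estimate that SAP 1.3 says may be exceeded.

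**The case against.** The strongest reply is that the scenario is not planned. The C-SSRS is scheduled only at Visits 1 to 4, and the contact calls in the Protocol's events schedule are for dosing, concomitant medication and reminders. Without an unscheduled form nothing resets, and a non-fatal event between visits falls within the next scheduled form's recall. Even with an unscheduled form, the documents do not say that it becomes the reference visit. SAP 6 also accepts remote C-SSRS forms as face-to-face, and every result is listed. All of this stands, and it limits the point to a gap that may turn out empty.

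Three stronger readings are tempting and not supported:

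- A reader might infer that an off-schedule event is in no count at all. SAP 2.3 substitution, the time-to-first number and, where the event is reported as an AE, the SAP 5.1 tables can each catch it.
- A reader might infer that a suicide between visits is lost because the recall window resets. After a death there is no later form, so that mechanism cannot operate. A suicide is an SAE by definition and must be recorded on the AE page (Protocol 12.3). On treatment, it enters the serious and fatal TEAE counts. What remains is narrower: SAP 5.6 does not say where completed suicide is taken from, and the TEAE window closes 1 day after the last dose while SAEs are collected for 30 days. The absence of the item from the reproduced form is also not proof that the eCRF lacks it.
- A reader might infer that the reported percentage is definitely too low. That needs positive unscheduled forms to exist, which the documents do not establish.

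The reply does not answer the missing any-time percentage, which is absent whether or not an unscheduled form is ever completed.

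**Conclusion.** The point holds in limited form. SAP 5.6 with SAP 2 and 2.3 can leave a positive unscheduled C-SSRS form out of the only planned suicidality percentage. Failure to recapture the event at the next scheduled visit further requires that the unscheduled form was treated as the last visit. Separately, and without any such assumption, the planned tables do not give the percentage of subjects positive at any time after baseline. The time-to-first summary does not replace it, because it has no percentage, excludes subjects positive at baseline and does not specify its forms.

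The effect of omitted unscheduled forms cannot be sized from the documents and may be zero. This is an inexpensive improvement to a descriptive safety table, best made before database lock.

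**What to change.** In SAP 5.6:

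1. Add a number and percentage of subjects positive at least once after baseline, for ideation, for behavior and for either, by treatment group and overall. Use all post-baseline C-SSRS forms, scheduled and unscheduled. The denominator is subjects with at least one post-baseline form, in keeping with SAP 2's rule of dividing by subjects with non-missing data. SAP 5.3 is the precedent for the row itself.
2. State that the time-to-first summary uses the same forms.
3. Take completed suicide from the AE/SAE page and show it as a separate line, including events reported after the 1-day TEAE window. Keep it apart from the form-based percentage, so that AE-page events do not enter a numerator whose denominator is subjects with forms.

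The by-visit table can stay as planned. The cost is some SAP wording, one extra derivation and a stated departure from the scheduled-visits-only rule for this table. It needs no new data collection. If the SAP is already final, SAP 1 requires the change to be documented in the CSR.

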8.1. Visit 1 (Baseline)

Visit 1 is expected to occur on the same day as the End-of-Study Visit (Visit 7) of Study IPX203-B16-02. After the subject provides consent for this study, carry over and record information from procedures at the End-of-Study Visit of IPX203-B16-02 as the baseline data for this study.

After the subject has signed the informed consent (and HIPAA authorization for subjects at US sites), complete the following procedures and assessments:

- Review and record study entry criteria ([Section 7](#)).
- Update the subject's medical history.
- Perform urine pregnancy test for females of childbearing potential.
- Complete the 12-Item Zarit Burden Interview (ZBI-12) ([Appendix M](#)).
- Administer the Early Morning Symptoms Questionnaire (EMSQ) ([Appendix N](#)).
- Contact the interactive web response system (IWRS) to dispense study drug.
- Instruct the subject on dosing.
- After Visit 1, contact subjects weekly for the first month and then approximately monthly thereafter to discuss the subject's dosing regimen. Record the subject's current IPX203 dose regimen.
- Instruct subjects to call the study site before making any changes to their IPX203 dosing regimen.
- Subjects may return for study drug resupply approximately every 1 to 2 months as needed.

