1.2 Study Design

Subjects who have successfully completed Study IPX203-B16-02 (A Randomized Controlled Study to Compare the Safety and Efficacy of IPX203 with Immediate-Release Carbidopa-Levodopa in Parkinson's Disease Patients with Motor Fluctuations) may be offered the opportunity to enroll in this 9-month, multicenter open-label study. The study consists of a baseline visit (Visit 1) followed by 3 visits (Visits 2 to 4) spaced at approximately 3-month intervals. For subjects who successfully complete Study IPX203-B16-02, the baseline visit (Visit 1) of this study will occur coincident with the End of Study (EOS) Visit 7 of the preceding study, (with an allowed window of + 7 days). After providing written informed consent (and signing Health Insurance Portability and Accountability Act [HIPAA] authorization for subjects at United States [US] sites only), confirmation of eligibility and baseline procedures will be performed. Subjects will be initially started on the final IPX203 dosing regimen that was determined during the IPX203 dose conversion period of Study IPX203-B16-02. Investigators are permitted to adjust the dosing regimen of IPX203 during this study to achieve the optimal balance of efficacy and safety and any changes will be recorded.

Subjects may continue to take their non-LD-containing PD concomitant medications (including dopamine agonists, amantadine, and selective monoamine oxidase-B (MAO-B) inhibitors [safinamide, rasagiline and selegiline]) during the study. Changes in doses or in dosing regimens of all non-CD-LD PD medications and/or the addition of new non-CD-LD PD medications will be captured. Supplemental CD and benserazide, apomorphine, and the addition of catechol-O-methyltransferase (COMT) inhibitors (eg, entacapone, opicapone, and tolcapone) can be initiated during the study.

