2.1 Definitions of Baseline

Baseline is defined as the last assessment obtained prior to the first dose of the open-label drug in the study IPX203-B16-03.

The study eCRF does not explicitly capture when the subject took the first open-label study drug dose. It will be assumed that this dose is taken on the day of Visit 1 after all study assessments.

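### The C-SSRS first-appearance summary looks back only one feeder-study interval, so a recurrence after an earlier B16-02 episode can be summarized as a first appearance

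*SAP*

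**What the plan says.** Four provisions have to be read together.

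- **Instrument.** SAP 5.6 states: "Columba Suicide Severity Rating Scale (“Since Last Visit” version) will be administered at each scheduled visit". Protocol Appendix B prints one form, headed "Since Last Visit", and no lifetime or screening version. Its overall behavior item asks whether "Suicidal behavior was present during the assessment period".
- **Baseline.** SAP 2.1: "Baseline is defined as the last assessment obtained prior to the first dose of the open-label drug in the study IPX203-B16-03". This is one assessment, not a history.
- **Source of the baseline form.** Protocol 8.1 tells sites to "carry over and record information from procedures at the End-of-Study Visit of IPX203-B16-02 as the baseline data for this study", and footnote a to Table 2 repeats this. Visit 1 is to coincide with feeder Visit 7, "with an allowed window of + 7 days" (SAP 1.2). The C-SSRS is not among the procedures that Protocol 8.1 lists to be done afresh at Visit 1.
- **Rule.** The time-to-first-appearance summary in SAP 5.6 is limited to subjects who develop ideation or behavior, explained as those who "do not have suicidal ideation or suicidal behavior at baseline, but report it during the study".

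SAP 5.6 also calls for counts and percentages of any ideation or behavior by visit, and for a listing of all results.

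**The concern.** The rule is there to keep pre-existing suicidality out of a summary that will be read as emergence on open-label IPX203. It screens with a form whose recall reaches back only to the preceding feeder visit. Someone with ideation earlier in B16-02 and none in its last interval passes the screen, and a later positive answer is then reported as a first appearance.

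Long-term safety is part of the study objective. All entrants had an IPX203 dose-conversion period in B16-02 and were then treated with either IPX203 or IR CD-LD, so an earlier episode could have arisen on either drug. If few subjects qualify for the summary, one or two such subjects could change how it reads.

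**Working it through.** The plan states no figure on this point, so the check is mainly of the text.

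**Step 1. What a negative baseline means.** A Since-Last-Visit form, used as the single baseline and taken at feeder Visit 7, says that nothing was reported since the preceding feeder visit. It says nothing about earlier parts of B16-02.

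**Step 2. How the rule sorts subjects.**

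| Earlier in B16-02 | Last feeder interval (baseline form) | Extension | SAP 5.6 first-appearance summary |
|---|---|---|---|
| negative | negative | positive | included; no earlier feeder positive |
| positive | negative | positive | included; a recurrence shown as a first appearance |
| either | positive | positive | excluded |
| either | either | negative | not in the set |

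Only the second row is at issue.

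**Step 3. Does another provision cover that row?**

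- The SAP adds the B16-02 study-entry baseline for MDS-UPDRS, PGI-S and CGI-S, PDQ-39, PAS, NMSS, PDSS-2 and EMSQ (SAP 4.2.1 to 4.2.6 and 4.2.9). It does not do so for the C-SSRS.
- Feeder adverse events resolved by Visit 1 become medical history (SAP 3.5), and adverse events that began in the feeder have their own summaries (SAP 5.1). A C-SSRS positive that was not recorded as an adverse event appears in neither.
- SAP 7 defers whole-exposure summaries of adverse events, vital signs and ECG to the Integrated Summary of Safety. It does not name the C-SSRS.

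Nothing in the two documents covers the row.

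**Step 4. Length of the look-back.** The feeder C-SSRS schedule is not given. The Protocol Introduction gives 13 weeks of therapy, and Protocol 6.4 places the end of dose conversion at feeder Visit 4. Assume that the 13 weeks run from Visit 4 to Visit 7.

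- With three equal intervals (a further assumption), the look-back is 13 / 3 = 4.3 weeks.
- If Visit 4 was the preceding C-SSRS visit, it is 13 weeks.
- If the form were instead repeated at a Visit 1 held after feeder Visit 7, it would be at most 7 days.

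The extension follows subjects for about 9 months.

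**Step 5. Illustration of how little such a window screens out.** Suppose that ideation episodes in a recurrently affected subject follow a Poisson process with λ episodes per year and no drug effect. The share of recurring subjects whose baseline window of w weeks is empty, and who therefore pass the screen, is exp(−λ × w / 52). For λ = 1 and w = 4.33, exp(−0.0833) = 0.92.

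| λ per year (assumed) | w = 4.3 weeks | w = 13 weeks |
|---|---|---|
| 0.5 | 96% | 88% |
| 1 | 92% | 78% |
| 2 | 85% | 61% |
| 4 | 72% | 37% |

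These are shares of recurring subjects, not of all cases in the summary. The documents give no rate from which to count either group.

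**The case against.** The strongest reply is that the SAP defines its own term. It explains developing suicidality as negative at baseline and then reported during the study, and it does not claim first-ever onset. This fits the study-wide baseline in SAP 2.1 and the treatment-emergent rule in SAP 5.1, both anchored to the first open-label dose. A baseline-referenced summary is a coherent choice for an extension study. That stands, and it is why the set should be kept. It does not answer the narrower point that the baseline screen is only one interval deep.

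Three further replies also stand. The feeder protocol is not available, so the use of the Since-Last-Visit form at feeder Visit 7 is an inference, though a fair one. Some earlier episodes will be visible as medical history or as adverse events that began in the feeder. And removing everyone with an earlier B16-02 positive would shrink the emergent set, which is less conservative for safety; for instance, a subject positive on IR CD-LD and again after moving to IPX203 would drop out.

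A reader might infer more than the documents support:

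- **That the reported times are wrong.** They run from this study's baseline to the first positive form after it, as defined. What is open to question is who is in the set and how the result is labelled.
- **That recurrent suicidality in general is counted as new.** Subjects positive in the last feeder interval are excluded.
- **That a given share of the reported cases would be recurrences.** No prevalence, recurrence or incidence rate is given, so any such share would only reflect the rates assumed.

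**Conclusion.** The point holds in a limited form. As written, SAP 5.6 cannot distinguish a subject with no B16-02 positive from one who was positive earlier in B16-02, negative in its last interval and positive again later. Both are summarized as a first appearance.

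The effect is confined to the descriptive time-to-first-appearance summary and its set of subjects. No test depends on it, and the by-visit counts and the listings are unaffected. The number of subjects concerned cannot be derived from the documents and may be zero. The conclusion rests on the carried-over feeder Visit 7 form being the Since-Last-Visit version, as SAP 5.6, Appendix B and the carry-over rule together imply. It is a cheap improvement, not a defect that threatens the study's conclusions.

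**What to change.** In SAP 5.6, leave the baseline-negative set as defined, so that no case is lost, and add two things:

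1. Split the summary by whether the subject had any positive ideation or behavior answer at any available B16-02 C-SSRS assessment before Visit 1: no prior positive, or recurrent.
2. Flag the same status in the C-SSRS listing.

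If B16-02 collected lifetime or screening history, show it separately, so that one remote positive does not move a subject into the recurrent group.

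The cost is a short addition to SAP 5.6, which SAP 1 says is to be finalized before database lock, and a merge of feeder C-SSRS data that the sponsor should already hold. No new data are collected. The small downside is that counts likely to be very low are divided further.
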